6. ADVERSE EVENTS: LIST AND REPORTING REQUIREMENTS

The following list of AEs (Section 6.1) and the characteristics of an observed AE (Section 6.2) will determine whether the event requires expedited (via Medwatch) reporting in addition to routine reporting.

6.1 Comprehensive Adverse Events and Potential Risks List (CAEPR)

The Comprehensive Adverse Event and Potential Risks list (CAEPR) provides a single, complete list of reported and/or potential adverse events (AE) associated with an agent using a uniform presentation of events by body system.

We have contacted CTEP and we have been informed that CTEP does not have a CAEPR list for 5-ALA (see Appendix D).

6.2 Adverse Event Characteristics

CTCAE term (AE description) and Grade

The descriptions and grading scales found in the revised NCI Common Terminology Criteria for Adverse Events (CTCAE) version 3.0 will be utilized for AE reporting. All appropriate treatment areas will have access to a copy of the CTCAE version 3.0. A copy of the CTCAE version 3.0 can be downloaded from the CTEP web site (http://ctep.cancer.gov).

Expectedness - AEs can be 'Unexpected' or 'Expected' for expedited reporting purposes only. 'Expected' AEs are listed in sections 11.1.2 and 11.1.3 of this protocol.

Attribution of the AE

Definite – The AE is clearly related to the study treatment.

Probable – The AE is likely related to the study treatment.

Possible – The AE may be related to the study treatment.

Unlikely – The AE is doubtfully related to the study treatment.

Unrelated – The AE is clearly NOT related to the study treatment.

6.3 Expedited Adverse Event Reporting

IRB NUMBER: 12-135

- 6.3.1 Phase 1 and phase 2 studies with investigational agents (Including hospitalization defined below):
 - For hospitalization only Any medical event equivalent to CTC grade 3, 4, or 5 which precipitated hospitalization (or prolongation of existing hospitalization) must be reported regardless of designation as expected or unexpected and attribution.
 - The FDA safety information and adverse event reporting system, Medwatch, FDA form 3500A will be used for reporting within 24 hours.
- 6.3.2 Expedited Reporting Guidelines Medwatch Reporting Requirements for Adverse Events That Occur Within 30 Days¹ of the Last Dose of the Investigational Agent on Phase 1 Trials

Phase 1 Trials								
Grade 1 Grade 2 Grade 2		Gra	de 3	Gra	de 3	Grades 4 & 5 ²		
	Unexpected and Expected	Unex- pected	Expected	Unexp with Hospitali- zation	oected without Hospitali- zation	Expo with Hospitali- zation	ected without Hospitali- zation	Unexpected and Expected
Unrelated Unlikely	Not Required	Not Required	Not Required	10 Calendar Days	Not Required	10 1 Calendar 1 Days 1	Not Required	24-Hour; 5 Calendar Days
Possible Probable Definite	Not Required	10 Calendar Days	Not Required	24-Hour; 5 Calendar Days	24-Hour; 5 Calendar Days	10 Calendar Days	Not Required	24-Hour; 5 Calendar Days

Adverse events with attribution of possible, probable, or definite that occur greater than 30 days after the last dose of treatment with an agent under a CTEP IND require reporting as follows:

AdEERS 24-hour notification followed by complete report within 5 calendar days for:

- Grade 3 unexpected events with hospitalization or prolongation of hospitalization
- · Grade 4 unexpected events
- Grade 5 expected events and unexpected events

Note: All deaths on study require both routine and expedited reporting regardless of causality. Attribution to treatment or other cause must be provided.

Expedited AE reporting timelines defined:

"24 hours; 5 calendar days" – The investigator must initially report the AE via Medwatch within 24 hours of learning of the event followed by a complete Medwatch report within 5 calendar days of the initial 24-hour report. "10 calendar days" - A complete Medwatch report on the AE must be submitted within 10 calendar days of the investigator learning of the event.

Any medical event equivalent to CTCAE grade 3, 4, or 5 that precipitates hospitalization (or prolongation of existing hospitalization) must be reported regardless of attribution and designation as expected or unexpected with the exception of any events identified as protocol-specific expedited adverse event reporting exclusions.

6.4 Routine Adverse Event Reporting

All Adverse Events must be reported in routine study data submissions. AEs reported

IRB NUMBER: 12-135

Although an AdEERS 24-hour notification is not required for death clearly related to progressive disease, a full report is required as outlined in the table.
December 15, 2004

through Medwatch must also be reported in routine study data submissions.

7. PHARMACEUTICAL INFORMATION

- 7.1 Drug (5-ALA) 5-ALA for oral administration will be provided by DUSA Pharmaceuticals New York, Inc., Valhalla, NY 10595.
- 7.2 Drug Availability The study drug 5-aminolevulinic acid will be provided by DUSA Pharmaceuticals New York, Inc., Valhalla, NY 10595.
- 7.3 Drug Ordering The study drug 5-aminolevulinic acid will be provided by DUSA Phamaceuticals, Inc. to the Memorial Medical Center or St. John's Hospital Pharmacy.
- 7.4 Drug Accountability The Investigator, or a responsible party designated by the Investigator, in cooperation with the Memorial Medical Center or St. John's Hospital Pharmacy will maintain a careful record of the inventory and disposition of all agents received from DUSA Pharmaceuticals, Inc.

8. CORRELATIVE/SPECIAL STUDIES

- 8.1 Assessment of Visual Tumor Discrimination
 - 8.1.1 Overall assessment of Tumor Discrimination With the tumor and tumor cavity exposed, the neurosurgeon will visualize the tumor and tumor cavity under white light and again under deep blue light illumination and assess the ability of fluorescent illumination to distinguish tumor from normal brain tissue. This subjective assessment will be graded by the neurosurgeon at the time of visualization from 0 to +++ (3+).

Grade	Definition	
0	No fluorescence. No difference between any of the tissues visualized.	No fluorescence
+	Low fluorescence. Red glow is barely distigushed from surrounding non-fluorescent tissue.	Weak fluorescence
++	Moderate fluorescence. Dull red glow of fluorescent tissue.	
+++	High fluorescence. Bright red glow of fluorescent tissue	Strong fluorescence

- 8.1.2 Surgical Assessment of Fluorescence in Biopsy Specimens:
 Each biopsy specimen taken for this trial under blue light will be graded for fluorescence intensity at the time of biopsy by the neurosurgeon on a scale of 0 to +++ (3+).
- 8.1.3 Pathologic Assessment of Biopsy Specimens:
 All biopsy specimens, including those taken from the bulk tumor, will be reviewed by a neuropathologist.

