12. STATISTICAL CONSIDERATIONS

- 12.1 Study Design/Primary Endpoints
 - 12.1.1 Establish a safe dose for oral 5-ALA administration NCI Common Toxicity Criteria will be used to quantify toxicity following 5-ALA administration. Special attention will be paid to rash, pruritis, hepatic transaminitis, nausea and vomiting. Based on previously reported German trial, a 30 mg/kg dose is anticipated to be as well-tolerated as 10 and 20 mg/kg doses.
 - 12.1.2 Determine the sensitivity and specificity of the Phase 1 recommended dose in discriminating between normal and malignant tissue intraoperatively.

Four methods are being employed to assess discrimination of tumor from normal brain tissue.

- The neurosurgeon will assess the ability to distinguish tumor from normal brain tissue under ultraviolet illumination and grade the discrimination from 0 to +++ (3+) (See Section 8.1.1). Although arguably the most relevant measure, this is also the most biased and difficult to corroborate measure.
- Under white light the neurosurgeon will assess and biopsy an area of obvious tumor and an area of obviously normal (but possibly edematous) non-eloquent brain. The neurosurgeon will then assess whether these

IRB NUMBER: 12-135

- areas correspond to areas of strong, weak or no fluorescence seen under blue light.
- Under blue light, the neurosurgeon will assess the areas of fluorescence in the tumor cavity and will biopsy areas of strong fluorescence, weak fluorescence and no fluorescence. It may not be necessary to repeat some of these biopsies if the area has already been biopsied under white light. The pathologist will score tumor involvement in each biopsy specimen.

These data will be placed in the following grids – first a 3x3 grid as follows for an analysis of correlation, specifically a Cohen's kappa will be calculated to assess the strength of agreement between fluorescence and tumor density:

Fluorescence vs. Tumor Density	Solid Tumor	Infiltrating tumor/normal brain	No tumor (edematous peritumoral normal brain)
High Fluorescence	(Number of areas identified)	(Number of areas identified)	(Number of areas identified)
Weak Fluorescence	(Number of areas identified)	(Number of areas identified)	(Number of areas identified)
No Fluorescence	(Number of areas identified)	(Number of areas identified)	(Number of areas identified)

Second, these data will also be placed in a simpler 2x2 grid for fluorescence sensitivity/specificity analysis:

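### The overall tumor-discrimination grade in 8.1.1 is anchored, at its two upper levels, on how bright the glow is and not on contrast with normal brain

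*Combined protocol and SAP*

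**What the plan says.** Section 8.1.1 defines an overall assessment made with the tumor and cavity exposed, first under white and then under deep blue light. Its purpose is to "assess the ability of fluorescent illumination to distinguish tumor from normal brain tissue". On scoring it says: "This subjective assessment will be graded by the neurosurgeon at the time of visualization from 0 to +++ (3"+). The table that follows has four definitions:

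- 0: "No fluorescence. No difference between any of the tissues visualized"
- +: "Low fluorescence. Red glow is barely distigushed from surrounding non-fluorescent tissue"
- ++: "Moderate fluorescence. Dull red glow of fluorescent tissue"
- +++: "High fluorescence. Bright red glow of fluorescent tissue"

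Section 4.1.2 and the Intra-Operative Data Sheet in Appendix C print the same definitions for single biopsy sites. Section 8.1.2 names the specimen-level quantity plainly: each specimen is "graded for fluorescence intensity at the time of biopsy by the neurosurgeon on a scale of 0 to +++ (3"+).

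In 12.1.2, the first method listed for assessing discrimination has the surgeon "grade the discrimination from 0 to +++ (3+) (See Section 8.1.1"). The same item ranks this, tentatively, as the measure of greatest relevance, and concedes that it is also the most prone to bias and the hardest to corroborate.

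**The concern.** Intensity and discrimination are different quantities. Intensity belongs to one piece of tissue. Discrimination is a comparison between two tissues and needs the appearance of normal brain as well as that of tumor. The documents use one table for both, and it fits neither fully.

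- For the overall grade, the appearance of normal brain has no written role at ++ or +++.
- For a single specimen, the second clause of grade 0 compares all the tissues in view. It cannot describe a non-fluorescent specimen taken from a cavity that fluoresces elsewhere.

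What is at stake is how a descriptive result can be read. A summary of overall grades would be presented as evidence on how well fluorescence separates tumor from brain, while its upper half records brightness.

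**Working it through.** The plan gives no figure for this grade, so there is nothing to reproduce. The only power statement, in 12.2, concerns a kappa and does not use this grade. The check is a comparison of texts followed by a small illustration.

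**Step 1. What each grade requires (8.1.1 table).**

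| Grade | Intensity wording | Refers to other tissue? |
|---|---|---|
| 0 | none | yes: no difference among tissues |
| + | low | yes: barely stands out from a non-fluorescent surround |
| ++ | moderate, dull | no |
| +++ | high, bright | no |

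The table changes meaning halfway up. Contrast enters the two lower grades only.

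**Step 2. Two hypothetical fields.** To compare the grade with a measure that does register selectivity, I use the 12.1.2 formulas, sensitivity = a/(a+c) and specificity = d/(b+d), plus the 2x2 kappa = (po − pe)/(1 − pe). The counts are assumed: 34 tumor areas and 34 tumor-free areas, 68 in all. The results do not depend on that number as long as the two groups are equal.

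*Field A: every area glows brightly.* a = 34, b = 34, c = 0, d = 0.
- Sensitivity = 34/34 = 1.00; specificity = 0/34 = 0.00.
- po = 34/68 = 0.50; pe = (68×34 + 0×34)/68² = 0.50; kappa = 0.00.
- Overall grade: +++ is the only definition met in full. The second clause of grade 0 is also met, but its first clause, absence of fluorescence, is not.

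*Field B: all tumor areas glow dully and no normal area glows.* a = 34, b = 0, c = 0, d = 34.
- Sensitivity = 34/34 = 1.00; specificity = 34/34 = 1.00.
- po = 68/68 = 1.00; pe = (34×34 + 34×34)/68² = 0.50; kappa = 1.00.
- Overall grade: ++.

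Read literally, the table can place a field with no discrimination above one with complete discrimination. The fluorescence classes printed beside the grades sharpen this: the Appendix C data sheet places ++ with + in the weak class, so field B shares a class with a glow that barely stands out.

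**Step 3. A less extreme pair.** Suppose tumor is +++ with normal brain ++, against tumor ++ with normal brain 0. In the first case the normal area counts as a false positive in the 2x2 grid; in the second it is a true negative. If the overall grade follows the brightness of the tumor, the first is graded +++ and the second ++. The table permits that reading but does not require it, because no rule says how site grades combine into the overall one. The comparison uses only the order of the grades, not differences between them.

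**Step 4. Where the grade goes next.** Section 12.1.2 specifies four grids: fluorescence against tumor density (kappa), fluorescence sensitivity and specificity, white-light sensitivity and specificity, and operative against MRI extent of resection (kappa). The overall grade enters none of them. The escalation table in 4.2.1 works on counts of dose-limiting toxicity and does not use it either.

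**The case against.** The strongest reply has four parts.

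*The scale can be read as contrast throughout.* The instruction asks about distinguishing tissues, and the two lower grades carry contrast wording, so ++ and +++ may be meant to continue from a dark surround. Sections 2.1.3 and 2.3 support this premise: normal brain forms little protoporphyrin IX, and tumor is described as red against dark brain. This stands in part. Where normal brain is dark, brightness and contrast move together and the reversal may be uncommon; the documents give no rate. But the upper anchors do not state the premise, and this grade is meant to assess it, not assume it.

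*A uniformly bright field might be graded 0.* A reader might infer that bright, non-selective fluorescence necessarily scores +++ as though it discriminated perfectly. The documents do not support that. The second clause of grade 0 fits such a field, and +++ is only the top grade, not a claim of perfect separation. What remains is ambiguity: two surgeons could defend opposite ends of the scale for one field.

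*The plan already discounts the measure.* It does, as biased and hard to corroborate. That discloses subjectivity. It does not disclose that the anchors describe a different quantity.

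*No decision depends on the grade.* A reader might infer that it could favor a higher dose. Section 4.1.1 does speak of a safest effective dose, and 11.5 has the monitoring committee look at fluorescence ratings after each cohort. Neither names the 8.1.1 grade or gives a rule for using it, and escalation follows toxicity counts. An effect on dose choice is not shown. This part of the objection stands.

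**Conclusion.** The mismatch is real and narrow. The first discrimination method in 12.1.2 is scored on a table whose ++ and +++ levels measure brightness alone. A bright, poorly selective field can therefore be graded at or above a dull, fully selective one, and a uniformly bright field has no unambiguous grade.

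The conclusion rests on the printed definitions. The illustrative fields are hypothetical; no passage reports or anticipates normal brain at ++ or +++, so the frequency of misgrading cannot be estimated from the documents.

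A reader might extend the point to the sensitivity and specificity objective. That would be wrong: those analyses rest on biopsy sites compared with pathology read blind to fluorescence, and they would show non-selective fluorescence if it occurred. No sample-size figure changes. The correction is worth making because it is cheap and because the plan gives this measure some prominence; no primary analysis depends on it.

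**What to change.** 1. Give 8.1.1 its own 0 to +++ anchors for contrast between tumor and normal brain, for example none, barely, moderately and clearly distinguishable. Let 12.1.2 refer to those.
2. Keep the intensity table for specimens (8.1.2, 4.1.2 and the Appendix C data sheet). Delete from its grade 0 the clause about differences between tissues, so that the grade describes the specimen alone.
3. For patients graded under the old table, tabulate the fluorescence grades of the obvious-tumor and obvious-normal sites as paired ordinal data, for example as a cross-table. Section 4.1.2 requires both sites to be graded, and the Appendix C forms have fields for them, so the summary is available wherever both were recorded. Do not subtract grades as if they were equally spaced. Present this as a supplement to the overall grade and not a replacement, because it largely recodes the second 12.1.2 method and loses the whole-field view.

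The cost is a change of wording and forms, with no new procedures or specimens. The downside is that overall grades given before and after the change are not directly comparable and must be reported separately.

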9. STUDY CALENDAR

Baseline evaluations are to be conducted within two weeks prior to start of protocol therapy. Scans and x-rays must be done within one week prior to the start of therapy. Adverse events will be recorded up to 30 days following surgery.

Pre-	Day 1	Day 2	Week 5
------	-------	-------	--------

23

	Study	(Surgery)		
5-ALA ^a		Х		
Informed consent	Х			
Demographics	Х			
Medical history	Х			
Physical exam	Х	Х		Х
Vital signs	Х	Х	X	Х
Concurrent Meds	Х	Х	X	
Height	Х			
Weight	Х	Х		Х
Performance Status	Х	Х		Х
Adverse Event Evaluation	х	Х	Х	×
CBC w/diff, platelets	Х	Х	X	Х
Serum chemistry	Х	Х	X	Х
EKG (as indicated)	Х			
MRI Brain gadolinium	Х		X	
B-HCG	Х			
Other correlative studies		Х		

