Abnormalities in liver function have been observed in patients following ingestion of 5-ALA. Webber et al. observed that almost one-quarter of all patients who retained 5-ALA had at least one abnormality in liver function tests.³⁷ This was unrelated to 5-ALA dose in that more patients receiving low doses (< 30 mg/kg) developed abnormalities than those receiving high doses. Significant variations in the time of appearance of the abnormalities were also noted (12 to 120 hr. postoperatively). In all cases, liver function tests returned to normal 2 months after receiving 5-ALA.

The most common complaint, due to Pp IX photosensitization, is a very unpleasant pricking, itching or burning sensation under the skin after exposure to the sun. A systemic load above 10 mg/kg is required to develop skin photosensitization (DUSA Pharmaceuticals) which lasts from approximately 24 to 48 hours following 5-ALA administration. It is for this reason that patients will be kept in subdued light conditions for 48 hours following surgery.

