4.1.3 Post-Operative Follow-up

Patients will be assessed for completeness of tumor resection within 24 hours following surgery using MRI both with and without gadolinium enhancement. A 24 post-surgical MRI within 24 hours of surgery is the standard of care for anyone undergoing surgical resection of a brain tumor. Subsequently, patients will be reimaged periodically to assess tumor progression according to the specific standard of care tumor treatment protocol determined by the Neuro-Oncologist. At these same intervals, when appropriate to the normal standard of care, routine liver function tests and physical examination will be performed.

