 - 11.4.2 Any data provided to Collaborator(s) for Phase 3 studies must be in accordance with the guidelines and policies of the responsible Data Monitoring Committee (DMC), if there is a DMC for this clinical trial.
- 11.5 Data Safety Monitoring Plan

A minimum of 3 to a maximum of *18 subjects will be enrolled in this study. Oral 5-ALA will be administered 2-3 hours prior to surgery in cohorts of three at five escalating doses (10, 20, 30, 40, or 50 mg/kg). (*Due to four patients receiving 40mg/kg rather than three, 19 total patients will be studied in phase 1. Protocol deviation approved by IRB on 17 Oct 2013.)

Study investigators and study personnel will carefully screen each patient for side effects and adverse events. Expected adverse events specific for 5-ALA are described in the Protocol (Section 11.1.2) and other expected adverse events are

27

listed in Section 11.1.3. Subjects will be assessed for any unexpected serious adverse events such as significant changes in vital signs, nausea, vomiting, rashes, skin eruptions, and any long term changes in liver function. Unauthorized disclosure of protected health information is also a risk of this study.

It is the responsibility of the Principal Investigator (PI), [name] to oversee the safety of this Phase I study. However, since [name] holds the IND for the investigational drug, an independent data safety monitoring committee (DSMC) has been assigned to this study. The DSMC will consist of [name] (hematology/oncology physician), [name] (oncology research study specialist), and [name] (neuropsychologist).

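### The study calendar schedules no serum chemistry or adverse-event evaluation between Day 2 and Week 5, so at least two-thirds of the 12 to 120 h liver-onset window cited in Section 2.1.4 has no scheduled test

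*Combined protocol and SAP*

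**What the plan says.** **Calendar (Section 9).** The columns are Pre-Study, Day 1 (surgery), Day 2 and Week 5. Serum chemistry and adverse-event evaluation are marked in all four. Physical exam is marked at Pre-Study, Day 1 and Week 5, and its Day 2 cell is blank. The text above the table says: "Adverse events will be recorded up to 30 days following surgery".

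**Liver (Section 2.1.4).** The cited experience is that "almost one-quarter of all patients who retained 5-ALA had at least one abnormality in liver function tests". On timing it says: "Significant variations in the time of appearance of the abnormalities were also noted (12 to 120 hr. postoperatively". On recovery: "In all cases, liver function tests returned to normal 2 months after receiving 5-ALA". The section describes the abnormalities as unrelated to dose and gives no grades.

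**Skin (Sections 2.1.4 and 4.3).** Photosensitisation is said to last roughly 24 to 48 h after dosing. Section 4.3 keeps patients in low light for at least 48 h from dosing; Section 2.1.4 counts the 48 h from surgery.

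**What the safety data are for.** Section 12.1.1, under the safe-dose objective, says: "Special attention will be paid to rash, pruritis, hepatic transaminitis, nausea and vomiting". Section 11.5 lists "any long term changes in liver function" among the things subjects will be assessed for. Section 4.2 makes an event of Grade 2 or higher dose-limiting if it is directly attributed to 5-ALA or its metabolites, and gives no observation period.

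**Later tests (Section 4.1.3).** At the periodic re-imaging intervals, "when appropriate to the normal standard of care, routine liver function tests and physical examination will be performed".

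**The concern.** The protocol states when liver abnormalities have been seen after this drug, then sets a calendar whose early blood draws stop before most of that period has passed. The next scheduled draw is about four weeks later. A transaminase rise can be silent, so unlike a symptomatic rash it may come to light only if blood is taken.

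Establishing a safe dose is the first primary objective (1.1.1). AST/ALT elevation and skin reaction are two of the three agent-specific expected events in Section 11.1.2, and either can be dose-limiting under Section 4.2. An event that is never measured cannot enter the count that drives the escalation table in 4.2.1 or the reported toxicity rates. Any error from this source therefore runs toward under-detection.

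Two smaller mismatches sit in the same table. The recording limit can close before the Week 5 evaluation that the calendar itself marks. And no physical exam is marked on Day 2 or at the end of light protection, although rash and pruritus are singled out in 12.1.1.

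**Working it through.** The plan states no figure on this point, so there is none to reproduce. The check is interval arithmetic on the documents' own times.

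**Inputs**
- Onset window: 12 to 120 h after surgery (2.1.4). Width = 120 − 12 = 108 h.
- Early chemistry: Day 1 and Day 2; the next is Week 5 (Section 9).
- Clock time of the Day 2 draw: not given. Let t be hours from surgery to that draw. Surgery is on Day 1, so t cannot exceed 48. I vary t from 12 to 48.
- Assumption: serum chemistry includes AST/ALT and bilirubin. The calendar does not say so; if it does not, coverage is worse.

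**1. Share of the onset window after the Day 2 draw** = (120 − t) / 108

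| t (h) | Hours left | Share |
|---|---|---|
| 12 | 108 | 100% |
| 24 | 96 | 96/108 = 89% |
| 36 | 84 | 84/108 = 78% |
| 48 | 72 | 72/108 = 67% |

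Most of the window follows the draw whatever its clock time. These are shares of hours, not of patients, because Section 2.1.4 does not say how onset is distributed over the range.

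**2. The next scheduled draw.** Week 5 is Days 29 to 35. It begins 28 × 24 = 672 h and ends 35 × 24 = 840 h after the start of Day 1, well past 120 h. Section 2.1.4 says only that tests were normal at 2 months. It does not say how many abnormalities had cleared by Week 5.

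**3. The recording limit against Week 5.** With surgery on Day 1, 30 days after surgery is Day 1 + 30 = Day 31. Days 32 to 35, four of the seven days of Week 5, lie beyond it.

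**4. Skin.** Forty-eight hours after a Day 1 dose falls on Day 3 at the same clock time. For an assumed dose between 06:00 and 14:00, Day 2 ends 48 − 6 = 42 h to 48 − 14 = 34 h after dosing. Light protection therefore ends on Day 3 or later, when nothing is scheduled. The last marked physical exam before Week 5 is on Day 1. A Day 2 adverse-event evaluation is marked.

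**5. Tests outside the calendar.** The liver tests in 4.1.3 accompany later re-imaging, are conditional on standard of care and have no fixed time. The screening for side effects in 11.5 names no blood test or time. Neither puts a scheduled test between Day 2 and 120 h.

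**The case against.** The strongest reply is that the gap is in scheduled assessments only. That is correct and limits the point in several ways.

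- **A reader might infer that nothing is collected from Day 3 to Day 28.** The documents do not support that. Events are recorded up to 30 days, Section 6.4 requires all adverse events to be reported, Section 11.5 has staff screen each patient, and Section 4.1 makes treatment inpatient. What is missing is a scheduled test or evaluation.
- **A reader might infer that skin reactions are missed.** This is not shown. The Day 2 adverse-event evaluation falls within about 48 h of dosing, and the complaint described in 2.1.4 is itching or burning, which a patient can report. The Day 1 exam might also follow the dose; the calendar does not say.
- **A reader might infer that long-term liver change has no scheduled data.** Week 5 chemistry is scheduled, and later tests may follow under 4.1.3. Section 6.3.2 also provides for some attributable events beyond 30 days, limited by grade and worded for a CTEP IND.
- **A reader might put the one-quarter rate into the escalation table and compute a distorted chance of escalating.** That would treat every ungraded abnormality as an attributable event of Grade 2 or higher and assume that none lasts to Week 5. Section 2.1.4 supports neither assumption. It also calls the abnormalities unrelated to dose, which weakens any claim that the choice between dose levels is distorted.
- **A reader might fault the Appendix C post-operative page for undated liver results.** The table layout is not clear enough in the extracted text to show this, and nothing here rests on it.

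What survives is the silent laboratory abnormality. Spontaneous reporting and bedside screening do not detect it, and no passage schedules a test in the later part of the cited window.

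**Conclusion.** The point holds as a mismatch between the calendar and the protocol's own toxicity summary. At least 67% of the cited liver-onset window, and 89% if the Day 2 draw is at 24 h, has no scheduled chemistry or adverse-event evaluation. A silent abnormality that starts after Day 2 and settles before Week 5 is measured by no scheduled test; one that persists could be seen at Week 5.

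The direction of the effect on the dose-limiting toxicity count and the toxicity rates is toward under-detection. Its size cannot be stated, because the cited abnormalities are of any grade, without attribution, and their distribution over time is not given.

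The 30-day limit can end before the Week 5 evaluation, and the blank physical-exam cell on Day 2 sits awkwardly with 12.1.1. Both are secondary. The conclusion rests on surgery being on Day 1, on Week 5 meaning Days 29 to 35, and on serum chemistry including the liver tests.

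**What to change.** Reconcile Section 9 with Sections 2.1.4, 4.3, 11.5 and 12.1.1, including whether the 48 h of light protection runs from dosing or from surgery. At minimum:

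1. Enter in the study data every post-operative liver test already drawn after Day 2, during the inpatient stay or standard-of-care follow-up, each with its date. Appendix C should provide for more than one dated result.
2. Word the adverse-event recording window so that it includes the Week 5 evaluation marked in the calendar.
3. State in the calendar that serum chemistry includes the liver tests, if that is intended.

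Whether and when any further blood test, adverse-event evaluation or physical exam is scheduled is for the sponsor to decide; no schedule is proposed here.

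The cost is a calendar and form amendment and some added data entry. The minimum changes need no new procedure.
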